Research Design and Methods 7 – Strategy for Data Analysis. All analyses will follow the intention-to-treat principle in that participants are included in the analyses regardless of the level of exposure to the intervention activities. In order to accomplish this analysis in patients who drop out of the study, we will employ a conservative imputation method such as last-value-carried-forward (LVCF). We will consider a P value less than or equal to 0.05 as statistically significant.

Specific Aim #1. Primary Outcome: Guideline Adherence. Guideline adherence will be determined by de-identified medical record and caregiver survey data. Outcomes are expressed as a percentage of applicable guidelines followed, which can be treated as continuously-scaled. In Table 4 of this application are examples of PD indicator process measures. Overall guideline adherence will be calculated as the mean percentage of eligible guidelines per patient that was adherent. Each of the 38 guidelines will also be analyzed individually.

All multivariate analyses will be preceded by bivariate analyses to describe relationships between key variables. First, descriptive statistics comparing the two arms on sociodemographic and clinical characteristics

(such as duration of PD) and on study outcome measures at baseline, using two-sample t-tests for continuous variables and χ^2 tests for categorical variables. We'll also compare baseline characteristics between participants who complete follow-up surveys and participants who do not complete follow-up surveys. Participants who do not finish the 18-month follow-up (or 24 months for the first 204 subjects; see below) due to bereavement or loss to follow-up will be excluded from the analyses but sensitivity analyses will include these participants.

An intention-to-treat analysis on all guideline adherence over time will be conducted using linear regression (or logistic regression when analyzing guidelines individually) with sampling weights using the sandwich variance estimator (robust variance estimator and Huber correction)⁵⁴⁻⁵⁵ as implemented in Stata, version 11. Intervention status, indicator variables for site and corresponding baseline measure will be included as independent variables in all models. Other potential important covariates will be selected in advance of data analysis to be included in the model.

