Although we anticipate modest attrition in this sample, we will use attrition weights for dependent variables obtained from the survey. Attrition weights will be derived using a logistic regression of the response status (completed study vs. not completed) on predictors, including demographics. The response probability will be predicted for each subject according to a fitted model. The weight will be the reciprocal of response probability.

The analysis also must account for the gap in the intervention over more than 6+ months for the subset of the first 204 patients enrolled in the trial and randomized to the intervention arm. Because of this, a 24 month survey was added to the study for all 204 of these individuals. The remaining 96 subjects who will be enrolled to obtain the final target enrollment of 300 but who will not experience this gap in the intervention will be followed for the pre-defined 18 months. In order to combine both of these "cohorts" into a complete analysis, a variable will be incorporated into the regression models to reflect the period of time the subject was off the intervention. For the subset out of the first 204 patients who were randomized to the intervention arm, this variable will take on a value of the number of months for this period; while for the second cohort of 96, this variable will take on the value of 0. (Also, any subject in the control ("usual care") group in either cohort will receive a value of 0 as well). This will be used as a linear adjustment variable to account for this anomaly in the way the intervention was administered, by incorporating it into a multiplicative interaction effect with intervention status. If this term is significant, then it will indicate that the delay of intervention affects the outcomes. The main effect of intervention status will remain as a separate term in the model.

Specific Aim #1. Secondary Outcome Measures:

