Using the data collected at baseline, 6-month, 12-month and 18-month (or 24 months for the first 204 subjects) follow-up, we will examine the difference in the change score (from baseline to 6 months, baseline to 12 months, and baseline to 18 months or 24 months) of the secondary outcome measures between two study arms. These measures will be analyzed using linear regression with sampling weights using the sandwich variance estimator (robust variance estimator and Huber correction).⁵⁴⁻⁵⁵ Intervention status, indicator variables for site and corresponding baseline measure will be included as independent variables in all models and potential covariates associated with each outcome measure will also be included as independent variables including the adjustment variable as noted above.

Sensitivity analyses will be performed to check the robustness of the main results or to explore other associations. These will include analyses using the last observed outcome measure carried forward to 18 months (or 24 months for the first 204 subjects) for those who do not reach the study end point, using only the 6 months of data, using only 12 months of data, and testing whether outcomes change significantly over time within each study arm.

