- g. **National VA Quality Leadership.** We will request to share our findings and “toolkit” with OQP for possible dissemination on their website. We would ask for opportunities to dialogue about ways to embed monitoring of one or two PD care indicators into national performance monitoring and improvement activities.
- h. **HSR&D Service.** The next phase of a QUERI process would be to monitor implementation and outcomes of a larger-scale study involving sites from multiple geographic regions, and we propose to develop an application for funding of such a research study, depending on this study’s findings.
- i. **Clinicaltrials.gov.** We will register the study on clinicaltrials.gov website, which will aid in dissemination of study findings, and update with study findings at the end of the trial.

Dissemination 3 – Estimated Budget. Development of study products and tools is part of the study budget and will require no additional resources. Travel to the National Consortium meetings and local VISN travel to give presentations will be supported through PADRECC funds. Other dissemination activities will occur through conference calls. Thus, there is no additional budget for these activities.

PROJECT MANAGEMENT PLAN (following page)

PROJECT MANAGEMENT SCHEDULE Updated November 2014 NCM-126

KEY	---- ongoing/scheduled	X deleted previously scheduled activity	# revised 2014						
Project Months	Year 1	Year 2		Year 3		Year 4		Year 5	
	5/1/12-9/30/12	10/1/12-4/30/13	5/1/13-9/30/13	10/1/13-4/30/14	5/1/14-9/30/14	10/1/14-4/30/15	5/1/15-9/30/15	10/1/15-4/30/16	5/1/16-9/30/16
	FY12	FY13	FY13	FY14	FY14	FY15	FY15	FY16	FY16
ACTIVITIES	0-6	7-12	13-18	19-24	25-30	32-36	37-42	43-48	49-53
Annual Advisory Board meeting				---		#		#	#
Steering Committee teleconf meetings		---	---	---	---	---	---	---	#
Weekly project and teleconf site meetings	---	---	---	---	---	---	---	---	#
Project internal DSMB meetings		X	---	---	---	---	---	---	#
Weekly mentor-mentee meetings	---	---	---	---	---	---	---	---	#
IRB approvals; annual renewal & Vendorizations	---		---		---		---		#
Patient identification from VISN 22 Data Warehouse & VHA National Data Systems (NDS)	---			X	#				
Vet patient lists with providers	---	---	---	---	---	#			
Recruit and enroll study participants	---	---	---	X	---	#			
Collect baseline measures	---	---	---	---	---	---			
Collect 6, 12, & 18-mo follow-up measures		---	---	---	---	---	---	---	---
Collect 24-mo follow-ups on first 204 enrollees							#	#	#

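### The months-off-intervention variable has no visit index, so the 6- and 12-month secondary models can adjust patients for a gap that had not yet begun

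*Combined protocol and SAP*

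**What the plan says.** Research Design and Methods 7, Specific Aim #1, deals with the interruption that affected intervention patients among the first 204 enrolled (the first cohort). It states that "a variable will be incorporated into the regression models to reflect the period of time the subject was off the intervention". For first-cohort intervention patients, "this variable will take on a value of the number of months for this period". The 96 later enrollees (the second cohort) and all controls get 0. The term is linear and is multiplied by intervention status; because controls are 0, that product is the same column as the variable itself. On interpretation: "If this term is significant, then it will indicate that the delay of intervention affects the outcomes".

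The terms fixed for every model are given as: "Intervention status, indicator variables for site and corresponding baseline measure will be included as independent variables in all models". Further covariates may be chosen in advance, but no cohort term is named.

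The Secondary Outcome Measures paragraph models change "from baseline to 6 months, baseline to 12 months, and baseline to 18 months or 24 months", with covariates "including the adjustment variable as noted above". Sensitivity analyses include "using only the 6 months of data, using only 12 months of data".

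Both versions of the Project Management Schedule mark the row "Collect 6, 12, & 18-mo follow-up measures" from the 10/1/12-4/30/13 block onward. They mark care management as deleted only in the 10/1/13-4/30/14 block.

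**The concern.** The variable is defined once per patient, as total months off, and is carried forward by reference. Taken as written, a patient whose month-6 survey preceded the gap still enters the month-6 model with about seven months off.

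Two things follow. First, the value is nearly constant in first-cohort intervention patients and 0 in everyone else, so it acts almost as a first-cohort flag within the intervention arm. The intervention coefficient is then close to second-cohort intervention patients against all controls, and patients with six uninterrupted months of care management add little to it. Second, the month-6 gap term becomes close to a comparison of the two cohorts within the intervention arm, yet the plan would read significance as an effect of the delay.

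The secondary outcomes (quality of life, self-efficacy, perceived care quality) make up part (b) of the Aim #1 hypothesis, so the 6- and 12-month results are likely to be reported and interpreted.

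**Working it through.** **Timing.** The deleted block 10/1/13-4/30/14 lasts about 6.9 months, which fits the gap of over six months described in the text. A month-6 survey done by 4/30/13 preceded it by at least five months. Enrolment by 3/31/13 puts month 6 before the gap. Recruitment is also marked in the 5/1/12-9/30/12 block; anyone enrolled then reached month 12 before the gap too.

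**The plan's own figure.** Table 3 gives 133 per arm for 0.4 SD at 90% power. The normal formula gives 2 × (1.960 + 1.282)² / 0.4² = 131.4, rounded up to 132; the t-based version gives 133. It reproduces. Without a gap term the SE is √(2/133) = 0.123 and the power is Φ(0.4/0.123 − 1.96) = 0.90.

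**Assumptions.** The documents give no enrolment dates. I count months from 5/1/12 and take uniform first-cohort enrolment t:
- starting at 2.5, 5 or 6 (mid-July 2012, 10/1/12, 11/1/12);
- ending at 17, 20.5 or 24 (9/30/13, mid-January 2014, 4/30/14);
- with the gap at 17-24, 18-24 or 17-23.

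Dropping the three combinations in which enrolment outlasts the gap leaves 24. Analysed patients per arm: 133, split by 204/300 into 90 first-cohort and 43 second-cohort.

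**Share whose month 6 precedes the gap** (t + 6 ≤ gap start):
- lowest: (11 − 6)/(24 − 6) = 5/18 = 28%;
- enrolment 10/1/12-9/30/13, gap filling the block: 6/12 = 50%;
- highest: (12 − 2.5)/(17 − 2.5) = 9.5/14.5 = 66%.

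A start as late as 2/1/13 with enrolment ending 9/30/13 gives 25 of 102, about a quarter. At month 12 the share is 0 to 3.5/14.5 = 24%.

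**Standard error of the intervention effect.** Regress the outcome on arm and gap G, with residual SD 1 and G = 0 in controls. Then SE² = 1/133 + 1/133 + Ḡ²/S_GG, where Ḡ and S_GG are the mean and corrected sum of squares of G in the intervention arm. Accrued G at month k is max(0, min(t + k, gap end) − max(t, gap start)).

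Worked case, enrolment 5-17 and gap 17-24:
- Fixed coding: ΣG = 630, ΣG² = 4410, Ḡ = 4.737, S_GG = 1425.8. SE = √(0.01504 + 0.01574) = 0.175, the same as √(1/43 + 1/133).
- Accrued, month 6: ΣG = 135, ΣG² = 539.9, Ḡ = 1.015, S_GG = 402.9. SE = √(0.01504 + 0.00256) = 0.133.
- Accrued, month 12: ΣG = 446.3, ΣG² = 2695.2, Ḡ = 3.355, S_GG = 1197.7. SE = √(0.01504 + 0.00940) = 0.156.
- Month 24: everyone has accrued all 7 months, so accrued and fixed coding coincide.

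**All 24 combinations.** Power is Φ(0.4/SE − 1.96). The last column is the share, in magnitude, of any first- versus second-cohort difference common to both arms that enters the intervention effect when no cohort term is fitted.

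| Coding | SE (SD) | Power at 0.4 SD | Cohort share |
|---|---|---|---|
| Fixed, any visit | 0.161-0.175 | 63-70% | 47-68% |
| Accrued, month 6 | 0.129-0.139 | 82-87% | 7-19% |
| Accrued, month 12 | 0.144-0.165 | 68-80% | 24-52% |
| Accrued, month 24 | 0.161-0.175 | 63-70% | 47-68% |

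With equal gap values the fixed-coding cohort share is 90/133 = 68%.

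**Separate simulation.** This used all 300 patients and 2,000 runs per start date, with an effect of 0.4 SD and an assumed loss of 0.04 SD per month off. Month-6 power was 66-69% with the single value and 88-91% with the accrued value. The mean intervention effect stayed at 0.40-0.41 under both. The month-6 gap coefficient, truly −0.04, averaged −0.005 to −0.010 with the single value and about −0.04 with the accrued value.

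**The case against.** **The plan never says the same value is used at each visit.** True. The variable is meant to reflect time off the intervention, and an analyst could set it to 0 for a patient not yet off. But one definition, referred back to without change, most naturally means one value, and leaving the choice to the analyst defeats a prespecified variable and interpretation.

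**Most of the precision cost belongs to the gap term itself.** This stands for the final visit. At 18/24 months the proposed coding leaves the SE and the cohort share where they were, and at month 12 it helps only in part. The argument for changing the definition is mainly about month 6.

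**The intervention effect is not shown to be biased.** Correct. A reader might infer bias from the miscoding, but the simulation shows none without a cohort difference, and the documents give no evidence of one. Site and baseline are adjusted for, and a cohort covariate could still be chosen in advance.

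**Accrued months depend on enrolment date.** Also correct. With common gap dates, the accrued term partly tracks calendar time, such as nurse start-up or learning, so it is not a clean delay effect either.

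**The 0.4 SD yardstick comes from the primary outcome.** It does. The plan claims no power for the 6- or 12-month secondary models, and adjusting for baseline would lower the residual SD. The power figures are illustrative.

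**The schedule is coarse.** Its dashes mean ongoing or scheduled, and baseline collection is still marked in the block where recruitment is deleted. The shares are therefore ranges under assumptions. That some patients are affected follows if the schedule was broadly kept.

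**Conclusion.** The point holds for the 6- and 12-month secondary change-score models, and for the 6-only and 12-only sensitivity analyses if those include the adjustment variable, which the plan does not say. Read as written, about 28-66% of first-cohort intervention patients are adjusted at month 6 for a gap they had not met (about a quarter if enrolment began as late as 2/1/13). The month-6 SE is roughly 0.16-0.175 SD where 0.13-0.14 was available, and the month-6 gap term cannot support the stated interpretation. These sizes rest on uniform enrolment, gap dates read from the schedule, 266 analysed and residual SD 1.

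A reader might go further and infer that the primary result or the final secondary comparison is compromised. The documents do not support that. The primary adherence model states no visit times, and by month 24 every first-cohort patient in the scenarios has accrued the whole gap, so the coding makes no difference there. This is a worthwhile correction to intermediate secondary analyses, not a threat to the main conclusion.

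**What to change.** In the gap paragraph and the Secondary Outcome Measures paragraph of Research Design and Methods 7, define the variable separately for each outcome time: the months of overlap between the site's administrative gap and the interval from randomisation to that outcome, and 0 for a patient whose gap had not begun, for the second cohort and for controls. Derive it from site gap dates and enrolment dates, not individual contact records, so that compliance does not enter the intention-to-treat model. State whether the 6-only and 12-only sensitivity analyses include it. Do not read the month-6 or month-12 term as a delay effect unless it uses this accrued variable, and note that it may still partly reflect calendar time.

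The cost is a few sentences and one derived variable per time point, from dates the study should already hold. The December 2015 schedule still shows analysis in 10/1/16-4/30/17, so this 12/5/2016 plan can be corrected before the final analysis. The downside is more reliance on linearity in months off, because patients surveyed during the gap carry graded values. A simple indicator that the gap had begun by the visit avoids this and keeps most of the gain: the month-6 SE is √(1/n₀ + 1/133), or 0.132-0.149 SD, where n₀ = 68 to 102 is the number of intervention patients with no gap yet.

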Our hypothesis is that this nurse-led, evidence-based, coordinated care management intervention will achieve: (a) higher adherence to PD quality indicators, and (b) better patient outcomes of health-related quality of life, patient self-efficacy and perceptions of care quality, relative to usual care over 18 months. To accomplish Specific Aim #1, veterans with PD will be recruited from Greater Los Angeles (GLA), Las Vegas, Loma Linda, Long Beach and San Diego Healthcare Systems, to achieve a target number of 300 enrolled and randomized in a 1:1 ratio to receive either the CHAPS care intervention, or care as usual (300 participants will be randomized equally into control and intervention groups, i.e. 150 in each group). Process measures and patient outcome data will be collected via structured telephone interviews with patients at baseline, 6, 12, and 18 months, and via abstraction of medical records. The first 204 participants will receive a 24-month survey to adjust for a 6-month delay in the project.

Specific Aim #2 is to (a) examine the extent of the nurse-led PD care management intervention implementation and factors associated with variations in degree of implementation, and (b) measure associated costs and cost offsets from the VA perspective, to provide regional and national VA leadership with data to guide decisions about the value of sustaining this PD care management intervention, and about feasibility of further dissemination within VA, if shown to be effective.

The hypothesis is that a process evaluation and a cost analysis will demonstrate that the intervention is feasible to implement and to sustain in terms of resource utilization. To achieve Specific Aim 2, three data collection methods will be used: (a) abstraction of data from: minutes of project meetings and staff satisfaction questionnaires of key staff including care managers and clinician champions on clinician position/role/responsibilities and impressions of and experiences with CHAPS, including suggestions for improvement, use of information systems, use of practice guidelines and templates, and

[figure not shown]

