Train all nurse care managers	---	---	---	---	---					
CHAPS care management activities		---	---	X	---	---	---	---	#	#
Intervention refinement based on NCM feedback				---	---					
MS Access programming of CHAPS tools	---	---	---	---						
Abstract medical records							X	X	#	#
Analyze data and prepare manuscripts				---		---			---	#
Produce annual project reports		---		---		---		---		#
DISSEMINATION ACTIVITIES										
a. Present at VA National PD Consortium mtg; PADRECC website			---		---		---		X	#
b. Present to VISN 22 leadership annually			---		---		---		X	#
c. Present to Nursing Research Adv Group			X		---		---		X	#
d. Apply to My HealtheVet Clinical Advisory Board to develop a Condition Center for PD									X	#
e. CIPRS to cyber seminars			X			---			X	#
f. Present to community organization leadership			X			---			X	#
g. Office of Quality Performance (OQP): PD Toolkit									X	#
h. Prepare proposal to HSR&D for roll out									X	#
i. Register with clinicaltrials.gov and update	---								X	#

Updated 7/14/2016

33

Mentors' Role Purpose, and Interactions with the PI:

1. [name], MPH: [name] will provide experienced and effective mentorship of [name] in all aspects of this study. [name], a neurologist and accomplished health services researcher, has mentored numerous post-doctoral students and physicians in health services research over the past 15 years. Drs. [name] and [name] have a long-standing professional relationship. [name] was the PI for a multi-site randomized controlled trial of a dementia care management program for which [name] was Project Manager while completing her PhD. Currently, they work together at the Southwest PADRECC; their offices are next to each other in Building 401 on the VA West LA Campus. [name] serves as Co-Principal Investigator and mentor on [name] HSR&D NRI funded pilot-study. [name] will meet twice weekly with [name] at the VA and will be available by telephone and email throughout the week to facilitate the study's success and [name] continued growth via this scientific endeavor.

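### Final-wave secondary-outcome models combine 24-month and 18-month scores and carry a gap variable that is 0 for all controls, with no named cohort term; any common change between months 18 and 24 then biases the arm effect

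*Combined protocol and SAP*

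**What the plan says.** The gap adjustment is set out under Research Design and Methods 7 (Strategy for Data Analysis), at the end of the primary-outcome text. Because care management lapsed for part of the first cohort, "a 24 month survey was added to the study for all 204 of these individuals". By contrast, the plan follows "The remaining 96 subjects who will be enrolled to obtain the final target enrollment of 300" for 18 months.

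- For first-cohort patients in the intervention arm, "this variable will take on a value of the number of months for this period", that is, the time off the intervention.
- The later enrollees get zero: "while for the second cohort of 96, this variable will take on the value of 0". Controls in both cohorts also get zero.
- The variable enters as an interaction with arm, and the arm main effect stays in the model. The plan will take a significant term as evidence that the delay affected outcomes.

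Specific Aim #1, Secondary Outcome Measures, then plans to "examine the difference in the change score (from baseline to 6 months, baseline to 12 months, and baseline to 18 months or 24 months". The named model terms are arm, site and the baseline value, plus unspecified covariates "including the adjustment variable as noted above". The gap variable is not redefined by visit, and neither cohort nor length of follow-up is named as a term.

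The Overview of Study Design and the Veteran survey section give the first 204 a 24-month survey in addition to the 18-month one. The hypothesis in Specific Aims concerns outcomes "relative to usual care over 18 months".

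**The concern.** The gap variable is non-zero only in the intervention arm. There it separates the first cohort from the second; among controls it separates nothing. At the final wave the cohorts also differ in follow-up by six months. The model can therefore absorb a month-18-to-24 change among intervention patients but not among controls, and the difference goes into the arm coefficient. In a neurodegenerative disease the natural direction for health-status outcomes is worsening, which would favour the intervention. The same change would appear as a gap effect and, under the plan's own rule, be reported as harm from the delay.

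A smaller problem concerns the 6-month models. The plan describes the gap as longer than six months, so a 6-month survey cannot yet reflect all of it, but the full length is entered.

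**Working it through.** **Plan's own figure.** A two-sided t-test at alpha 0.05 and 90% power gives 235, 173 and 133 per arm for effects of 0.3, 0.35 and 0.4 SD, as in Table 3. That table is for the primary outcome. No power figure is stated for the secondary outcomes.

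**Inputs.** From the plan: 204 and 96 patients at 1:1, so about 102 + 102 and 48 + 48, and the gap coding above. Assumed: residual SD 1; site and baseline terms left out; no attrition; no true arm or gap effect; a worsening δ between months 18 and 24 that is the same in both arms (higher scores better); and three gap patterns, because the plan gives no individual lengths.

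**Step 1: rank.** Since the gap is 0 in every control, gap and gap × arm are the same column (rank 3 of 4). One gap term is estimable.

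**Step 2: bias with a constant gap.** The gap term removes the 102 first-cohort intervention patients from the arm coefficient. What remains is the mean of 48 second-cohort intervention patients (18 months) minus the mean of 150 controls, of whom 102/150 = 68% are measured at 24 months:

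- arm coefficient = 0 − (−0.68δ) = +0.68δ
- gap coefficient × gap length = −δ
- SE(arm) = √(1/48 + 1/150) = 0.166

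**Step 3: type I error.** With z = bias/SE, the rejection probability is Φ(z − 1.96) + Φ(−z − 1.96). For δ = 0.2 and a constant gap, z = 0.136/0.166 = 0.82, which gives 13.0%.

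| Assumed gap | Bias in arm effect | SE (SD) | Type I error at δ = 0.1 / 0.2 / 0.3 / 0.4 SD |
|---|---|---|---|
| Constant, 7 months | 0.68δ | 0.166 | 6.9 / 13.0 / 23.3 / 37.5% |
| Uniform, 6–9 months | 0.65δ | 0.164 | 6.8 / 12.5 / 22.1 / 35.4% |
| Uniform, 0–9 months | 0.33δ | 0.142 | 5.6 / 7.5 / 10.7 / 15.3% |

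Over the same δ range, with no true gap effect, the test of the gap term rejects 8.8% to 62.8% of the time (constant gap) or 6.8% to 35.7% (0–9 months).

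**Step 4: alternative models.** Power is at 0.4 SD with all 300 patients; figures involving the gap term are for the constant gap.

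| Model | Bias | SE (SD) | Power |
|---|---|---|---|
| Arm only | 0 | 0.115 | 93% |
| Arm + gap (as written) | 0.68δ | 0.166 | 67% (ignoring bias) |
| Arm + gap + cohort | 0 | √(1/48 + 1/48) = 0.204 | 50% |
| Arm + cohort | 0 | √(1/150 + 1/150) = 0.115 | 93% |

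**Step 5: timing at 6 months.** The row "CHAPS care management activities" in the Project Management Schedule is marked deleted for 10/1/13 to 4/30/14. If the gap began on 1 October 2013 and the 204 were enrolled evenly through September 2013, a 6-month survey before the gap requires enrolment before April 2013. That is 9/15 = 60% for a July 2012 start, 5/11 = 45% for November 2012, and 0/5 = 0% for May 2013. The schedule does not settle which: follow-up collection starts in the 10/1/12 column, but the 24-month row starts only in the 5/1/15 column, which points to enrolment from about May 2013.

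**The case against.** **Pooling is harmless under 1:1 randomization.** Correct for the pooling alone: the arm-only model has zero bias. A reader might infer that mixing 18- and 24-month scores is itself the fault. It is not; the bias comes from pairing the gap term with no cohort term.

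**The mix is deliberate.** The extra survey was added to compensate for the delay, and setting 24 months against 18 plausibly aligns time on intervention. That is a fair reason to keep the mix, but it does not remove the need for a cohort term.

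**The plan allows further covariates.** It does, so one cannot say that no cohort term will be fitted, only that none is named or committed to.

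**δ is assumed.** This stands. The documents give no month-18-to-24 change, and for self-efficacy or perceptions of care, progression is less obviously relevant than for quality of life. Hence a range is shown rather than one value.

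**The 6-month surveys.** It is tempting to say that a known share of 6-month scores preceded the gap, or that the miscoding biases the 6-month arm effect. The documents establish neither. The share runs from 0% to 60% depending on how an inconsistent planning table is read. Follow-up is equal at 6 months, so without an underlying cohort difference the miscoding mainly dilutes the gap coefficient and costs precision.

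**Other waves are unaffected.** The 6- and 12-month contrasts, and the sensitivity analyses limited to those waves, do compare equal follow-up. They do not repair the final-wave result.

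**Conclusion.** The point holds for the final-wave models as written. A common month-18-to-24 change δ enters the arm coefficient at 0.33δ to 0.68δ, depending on how much gap lengths vary, and any worsening favours the intervention. For δ of 0.1 to 0.4 SD, type I error runs from 5.6% to 37.5% across those gap patterns. If δ is zero for an outcome, this bias is zero. The planned reading of a significant gap term is unsafe, because that term also absorbs the difference in follow-up. Both defects disappear once a cohort indicator is fitted in both arms.

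At 6 months the full gap length overstates time off the intervention whether the survey fell before or partway through a gap of more than six months. That is a coding fault with a lesser consequence. The figures rest on planned counts before attrition, balanced arms within cohort, and a simplified model without site and baseline terms.

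**What to change.** In Strategy for Data Analysis and in Secondary Outcome Measures:

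1. Add a cohort indicator (first 204 versus last 96), for both arms, to every model that uses the final wave or the gap variable.
2. Make arm + site + baseline + cohort the main model. Report the gap-term model, with cohort included, as secondary.
3. Count gap months only up to each survey date, with 0 where the survey precedes the gap.
4. Use the 18-month score, planned for all 300, as the common final time point, and report 24 months separately for the first 204. If the 18/24-month mix is kept to align time on intervention, the cohort indicator is essential.

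This needs plan wording and recoding from survey dates that the study registry already holds. A single repeated-measures model is not required.

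The costs are these. The main model estimates an effect averaged over patients with and without the gap. An 18-month end point gives the first cohort less time on intervention. The secondary gap-plus-cohort model is less precise than the gap model as written: with a constant gap, SE about 0.20 against 0.17 SD and power at 0.4 SD about 50% against 67%. The main arm + cohort model keeps SE 0.115 SD and 93% power with all 300 patients, before attrition.
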